1. SYNOPSIS

Protocol Title: An open-label study in healthy male subjects, to determine the excretion balance and pharmacokinetics of [¹⁴C]-GSK2269557, administered as a single intravenous microtracer (concomitant with an inhaled non-radiolabelled dose) and a single oral dose.

Short Title: Absorption & elimination of radiolabelled GSK2269557

Rationale: GSK2269557 is a potent and highly selective PI3K-delta inhibitor, being developed as an anti-inflammatory agent for the treatment of COPD and other inflammatory lung diseases. The pharmacokinetics, absorption, distribution and metabolism of GSK2269557 have been studied in animals, *in vitro*, and in previous clinical studies; however, the elimination routes, intravenous pharmacokinetics and metabolic pathways of GSK2269557 have not been fully elucidated in humans. This open-label study in 6 healthy male participants will assess the excretion balance of the treatment, intravenous clearance and volume of distribution, and estimate its inhaled and oral bioavailability. Participants will receive [¹⁴C] radiolabelled GSK2269557, administered as a single microtracer by IV infusion (concomitant with an inhaled non-radiolabelled dose of GSK2269557), and a single dose of [¹⁴C]-GSK2269557, administered as an oral solution. Samples from this study will also be used to characterise and where possible quantify the metabolites of GSK2269557 in plasma, urine, faeces and duodenal bile.

Objectives and Endpoints:

Objective	Endpoint
Primary	

 To determine total radioactivity (drug related material) in plasma following a single IV microtracer of [¹⁴C]-GSK2269557 (concomitant with an inhaled non-radiolabelled GSK2269557 dose) and a single oral dose of [¹⁴C]-GSK2269557. 	
 AUC (0-inf), AUC (0–t), Cmax, tmax, t1/2 of total drug-related material (radioactivity) in plasma.

 To determine the rate and extent of excretion of total radioactivity in urine and faeces and the total recovery of radioactivity following a single IV microtracer of [¹⁴C]-GSK2269557 (concomitant with an inhaled non-radiolabelled dose) and a single oral dose of [¹⁴C]-GSK2269557. 	
 Urinary and faecal cumulative excretion as a percentage of the total radioactive dose administered over time.

Objective	Endpoint
Secondary	

 To determine parent GSK2269557 concentration in plasma following a single IV microtracer of [¹⁴C]-GSK2269557 concomitant with an inhaled non-radiolabelled GSK2269557 dose and a single oral dose of [¹⁴C]-GSK2269557. 	
 AUC(0-inf), AUC(0-t), Cmax, tmax, and t_{1/2} of parent GSK2269557 and [¹⁴C]-GSK2269557¹ in plasma. Volume and clearance of parent [¹⁴C]-GSK2269557¹ after IV dose only.

 To estimate the absolute bioavailability of GSK2269557 following inhaled and oral administration. 	
 Oral and inhaled F (absolute bioavailability).

 To evaluate the safety and tolerability of GSK2269557 after single IV, oral and inhaled doses in healthy participants. 	
 Incidence of adverse events. Laboratory safety, electrocardiogram (ECG) and vital signs parameters.
Exploratory	

 To generate samples that will be used to characterise the metabolic profile of GSK2269557 in plasma, urine, faeces, and duodenal bile (following IV dose only), following a single IV microtracer of [¹⁴C]-GSK2269557 (concomitant with an inhaled non-radiolabelled dose) and a single oral dose of [¹⁴C]-GSK2269557 (these analytical investigations will be conducted and the results reported under a separate Platform Technology Services (PTS) In vitro/In vivo Translation (IVIVT), GlaxoSmithKline protocol). 	
 Characterisation and quantification of metabolites in plasma, urine, faeces, and duodenal bile (these analytical investigations will be conducted and the results reported in a separate GSK PTS IVIVT protocol).

¹ For measured concentrations of GSK2269557 in blood plasma, the nomenclature [¹⁴C]-GSK2269557 describes the parent GSK2269557 concentration derived via analysis by liquid chromatography (LC) + Accelerator Mass Spectrometry (AMS), whereas GSK2269557 describes the parent GSK2269557 concentration derived via liquid chromatography-tandem mass spectrometry (LC/MS).

Overall Design: This is an open-label, single centre, non-randomised, 2-period single-sequence crossover, mass balance study to investigate the recovery, excretion, and pharmacokinetics (PK) of [¹⁴C]-GSK2269557 administered as a single IV dose (concomitant with an inhaled non-radiolabelled dose) and a single oral dose, in healthy male participants.

Number of Participants: 6 healthy male participants.

Treatment Groups and Duration: Each participant will participate in the study for up to 11 weeks, and will have a screening visit, 2 treatment periods, and a follow-up visit. In each treatment period, participants will be resident in the unit from the morning before Day 1 (Day -1).

On Day 1 of treatment period 1, after an overnight fast of at least 8 h, each participant will take 1000 µg non-radiolabelled GSK2269557 by inhalation. Within 5 min after the inhalation, participants will receive 10 µg [¹⁴C]-GSK2269557 (approximately 22.2 kBq; 0.6 µCi) by IV infusion over 15 min. Following dosing, blood, duodenal bile, urine and faecal samples will be collected up to 168 h after dosing (Day 8). Participants will be discharged on Day 8 after completion of the 168-h post-IV dosing sample collection. There will be a washout of at least 14 days after inhaled and IV dosing before participants take the oral dose of [¹⁴C]-GSK2269557 in treatment period 2.

On Day 1 of treatment period 2, after an overnight fast of at least 8 h, each participant will take 800 µg [¹⁴C] -GSK2269557 (approximately 1850 kBq; 50 µCi) as an oral solution. Following dosing, blood, urine and faecal samples will be collected for a minimum of 168 h (up to Day 8), but could be up to 336 h (Day 15) or longer after dosing, depending on the amount of radioactivity excreted by each participant. Liquid scintillation counting (LSC) will be performed daily on 24-h urine collections and 24-h faecal homogenates after Day 6 (at 144 h and 168 h from dosing).

- If less than 1% of the dose is excreted in each 24-h period on Day 6 (120-144 h) and Day 7 (144-168 h) for a given participant, that participant may be discharged as early as Day 8 (after the LSC results are available), and no further samples will be collected.
- If excretion is higher than 1%, or if the results are inconclusive, in each 24-h period on Day 6 (120-144 h) and Day 7 (144-168 h) for a given participant, the participant will remain at the unit, and urine and faecal collections will continue at 24-h intervals, for up to 7 days (until the morning of Day 15). If less than 1% of the dose is excreted in any of the 24-h periods between Day 7 and Day 15, that participant will be discharged. All remaining participants will be discharged from the unit on Day 15.
- In the unlikely event that excretion is still higher than 1% upon discharge on Day 15, the participants will continue to collect faecal samples only, at home, at 24-h intervals. Samples will be returned to the unit every 2-3 days for analysis.

Bile samples will be collected after the IV microtracer only, using Entero-Test string sampling of duodenal bile (subject to commercial availability).

Plasma samples will be prepared (from collected blood samples) to measure parent drug (GSK2269557, [¹⁴C]-GSK2269557) and total radiolabelled drug-related material. Urine and faecal samples will be collected to measure total radiolabelled drug-related material. Samples of plasma, urine, bile and faeces will also be transferred to a separate study to characterise and, where possible, quantify metabolites in those matrices.

Safety data will include AE reporting, 12-lead ECG, vital signs, and laboratory safety tests.

2. SCHEDULE OF ACTIVITIES (SOA)

Schedule of activities for Treatment Period 1

Procedure	Screening		Treatment Period 1 (IV and inhaled dosing)								
			Day								
	-30 to -1	-1	1		2	3	4	5	6	7	8
			Pre-dose	Post-dose 0–16 h	24 h	48 h	72 h	96 h	120 h	144 h	168 h
Admission to Unit		X									
Informed Consent	X										
Discharge from Unit											X
Demographics	X										
Full Physical Exam	X										
Brief Physical Exam		X									X
Inhaler training ¹		X									
Medical/medication/drug/alcohol history	X										
HIV, Hep B and Hep C screen	X										
Alcohol and cotinine tests, and urine drugs of abuse ²	X	X									
Laboratory safety tests	X	X	X		X						X
12-lead ECG ³	X	X	X	X	X						X
Vital signs (HR and BP) ³	X	X	X	X	X						X
Inhaled dose				X							
IV infusion				X ⁴							
Local tolerability assessment ⁵				X	X	X					
Blood samples for background radiation, total radioactivity, [¹⁴ C]-GSK2269557 analysis and cold GSK2269557 analysis ⁶	X ⁷	X ⁷	X ^{7,8}	X	X	X	X	X			X

Procedure	Screening		Treatment Period 1 (IV and inhaled dosing)								
			Day								
	-30 to -1	-1	1		2	3	4	5	6	7	8
			Pre-dose	Post-dose 0-16 h	24 h	48 h	72 h	96 h	120 h	144 h	168 h
Blood samples for metabolite profiling			X ⁸	X ⁹							
Urine collection ^{10,11}			X	X	X	X	X	X	X	X	X
Faecal collection ^{12,13}			X ¹³	X	X	X	X	X	X	X	X
Entero-Test ¹⁴			<————→								
Meals ¹⁵				X							
AE/concomitant medication review ¹⁶			←————→								

1. Training conducted by reviewing the Patient Information Leaflet with the participant. Additional training may be conducted at the discretion of the investigator.
2. Breath test will be performed to check alcohol consumption. Both CO breath tests and urine cotinine tests will be performed to check smoking state.
3. Triplicate measurements will be taken at screening and pre-dose on Day 1; single measurements will be taken at 6 h post-dose on Day 1 and at all other time points. Mean of triplicate measurements to be used as baseline.
4. IV infusion to begin as soon as possible (but within 5 min) after the start of the inhaled dose.
5. Local tolerability assessment for injection site reactions will be performed immediately after the end of dosing on Day 1 at 6 and 12 h, and on Days 2 and 3.
6. Sampling times relative to the start of the IV infusion. Blood samples for total radioactivity, [¹⁴C]-GSK2269557 analysis and cold GSK2269557 analysis will be taken: pre-dose and at 0h (post inhalation and pre-IV infusion), at the end of infusion and at 0.33, 0.5, 0.75, 1, 2, 3, 4, 6, 8, 12, 16, 24, 48, 72, 96 and 168 h after the start of infusion.
7. Background radiation sample taken at screening, Day -1 and pre-dose only.
8. An additional pre-dose blood sample may be taken from 1 participant for preparation of a plasma shipment control (details provided in the SRM).
9. Blood samples for plasma metabolite profiling will be collected at 0.5 h and 4 h after the start of the IV infusion.
10. An aliquot from each urine collection will be taken for metabolic profiling (separate study).
11. Sampling times relative to the start of the IV infusion. Urine will be collected at pre-dose, 0-6 h, 6-24 h then over 24 h collection periods as follows: 24-48 h, 48-72 h, 72-96 h, 96-120 h, 120-144 h, 144-168 h.
12. An aliquot from each homogenised faecal collection will be taken for metabolic profiling (separate study).
13. Sampling times relative to the start of IV infusion. The pre-dose faecal collection sample can be collected up to 24 h pre-dose. Afterward faeces will be collected over 24 h collection periods as follows: 0-24 h, 24-48 h, 48-72 h, 72-96 h, 96-120 h, 120-144 h, 144-168h.
14. Entero-Test string device will be swallowed at approximately 3.5 h pre-dose (start of inhaled dose) while participants are in a fasted state and the string removed at about 2.5 h post-dose on Day 1. At about 0.5 h post-dose (i.e. 2 hours before string withdrawal) a food cue will be used to stimulate gall bladder emptying).

15. Meal times are 30 min, 4 h and 10 h post dose on Day 1. On all other days, meals will be served at the standard times for the unit.
16. AEs and SAEs will be collected from the signing of the ICF until the follow-up visit. However, any SAEs related to study participation or a GSK concomitant medication will be recorded from the time a participant consents to participate in the study and until the final follow-up visit contact.

Schedule of activities for treatment period 2

Procedure	Treatment Period 2 (Oral dosing)									Follow-up (7-14 days post-last dose) ^{2,3}	
	Day										
	-1	1 ¹		2	3	4	5	6	7		
		Pre-dose	Post-dose 0-16 h	24 h	48 h	72 h	96 h	120 h	144 h	168 h	
Admission to Unit	X										
Discharge from Unit ^{2,3}									X		
Drugs of abuse	X										
Alcohol and cotinine tests ⁴	X										
Brief Physical Exam		X								X	
Laboratory safety tests	X	X		X					X	X	
12-lead ECG	X	X	X ⁵	X					X	X	
Vital signs (HR and BP)	X	X	X ⁵	X					X	X	
Oral dose			X								
Blood samples for total radioactivity, [¹⁴ C]-GSK2269557 analysis and cold GSK2269557 analysis		X ⁶	X	X	X	X	X		X		
Blood samples for metabolite profiling		X	X ⁷	X							
Urine collection ^{8,9}		X	X	X	X	X	X	X	X		
Faecal collection ^{10,11}		X ¹¹	X	X	X	X	X	X	X	X ¹²	
Meals ¹³			X								

Procedure	Treatment Period 2 (Oral dosing)									Follow-up (7-14 days post-last dose) ^{2,3}	
	Day										
	-1	1 ¹	2	3	4	5	6	7	8		
AE/concomitant medication review ¹⁴		←	→								

1. There will be a washout of at least 14 days between dosing in treatment period 1 and 2.
2. If less than 1% of the dose is excreted in each 24 h period on Day 6 (120-144 h) and Day 7 (144-168 h) for a given participant, the participant may be discharged as early as Day 8 (after the LSC results are available), and no further samples (apart from for laboratory safety tests) will be collected. Follow-up procedures may be done at discharge and procedures scheduled for Day 8 and follow up will only be done once.
3. If excretion is higher than 1%, or if the results are inconclusive in each 24-h period on Day 6 (120-144 h) and Day 7 (144-168 h) for a given participant, that participant will remain at the unit, and urine and faecal collections will continue at 24-h intervals, for up to 7 days (until the morning of Day 15), until excretion is less than 1%. All remaining participants will be discharged from the unit on Day 15. Follow-up procedures may be done at discharge. In the unlikely event that excretion is still higher than 1% upon discharge on Day 15, participants will continue to collect faecal samples only, at home, at 24-h intervals. Samples collected at home will be returned to the clinic every 2-3 days.
4. Breath test will be performed to check alcohol consumption. Both CO breath tests and urine cotinine tests will be performed to check smoking state.
5. Vital signs and ECG will be taken 6 h post dose.
6. Sampling times relative to the oral dose. Blood samples for total radioactivity, [¹⁴C]-GSK2269557 analysis and cold GSK2269557 analysis will be taken: pre-dose and at 0.25, 0.5, 0.75, 1, 2, 3, 4, 6, 8, 10, 12, 16, 24, 48, 72, 96 and 168 h post-dose.
7. Blood samples for plasma metabolite profiling will be collected at 2 h and 6 h post-[¹⁴C]-GSK2269557 oral dose.
8. An aliquot from each urine collection will be taken for metabolic profiling (separate study).
9. Urine will be collected at pre-dose, at 0-6 h, 6-24 h then over 24 h collection periods as follows: 24-48 h, 48-72 h, 72-96 h, 96-120 h, 120-144 h, 144-168 h.
10. An aliquot from each faecal collection will be taken for metabolic profiling (separate study).
11. The pre-dose faecal sample can be collected up to 24 h pre-dose. Afterward faeces will be collected over 24 h collection periods as follows: 0-24 h, 24-48 h, 48-72 h, 72-96 h, 96-120 h, 120-144 h, 144-168 h.
12. If dose excretion is still higher than 1% after day 15 the participants will continue to collect faecal samples only, at home, at 24-h intervals until excretion is less than 1%.
13. Meal times are 4h and 10h post dose on Day 1. On all other days, meals will be served at the standard times for the unit.
14. AEs and SAEs will be collected from the signing of the ICF until the follow-up visit. However, any SAEs related to study participation or a GSK concomitant medication will be recorded from the time a participant consents to participate in the study and until the final follow-up visit contact.

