3.3.1. Risk Assessment

Potential Risk of Clinical Significance	Summary of Data/Rationale for Risk	Mitigation Strategy
Investigational Product [e.g. GSK2269557]		
Radioactivity exposure risk (¹⁴C)-GSK2269557)	
The total effective dose associated with IV and oral administrations of [¹⁴C]-GSK2269557 is 0.75 mSv. That effective dose is within the lower end of WHO recommendation (0.5 to 5 mSv) for Category II projects, which is considered to be within dose limits for members of the public. The total effective dose is also below the GlaxoSmithKline Global Safety Board level of radiation which would require specific additional justification and exemption (10 mSv).
	
Participants will be monitored for recovery of radioactivity throughout the study.

Bronchospasm	
Can potentially occur with any inhaled treatment.
	
All doses of study treatment will be administered in the clinical pharmacology unit in the presence of trained clinical staff.
 
Treatment with a short-acting inhaled bronchodilator will be available. GSK2269557 should be discontinued immediately, the participant assessed and, if necessary, an alternative therapy instituted as deemed appropriate by the investigator or the attending physician. Participants will be withdrawn from the study.

Potential Risk of Clinical Significance	Summary of Data/Rationale for Risk	Mitigation Strategy
Mucosal irritancy	Detected in 13 week toxicology study in the dog.	Participants will be regularly monitored for AEs. No evidence of mucosal irritancy has been seen so far in clinical studies.
Exposure to GSK2269557	The total systemic exposure of GSK2269557 from the combined IV microtracer (10 µg) and inhaled dose (1000 µg) is predicted to be below the systemic exposure from the highest dose of GSK2269557 tested in previous human studies (a single inhaled nebulised dose of 6400 µg). The oral dose to be tested is 800 µg. Overall GSK2269557 has been well tolerated in previous clinical studies and has an acceptable safety profile. The most commonly observed AEs have been cough and headache.	In addition to taking samples for pharmacokinetic analysis of GSK2269557, pharmacodynamic markers of GSK2269557 will be monitored: HR and QTc measurements will be taken, haematology and clinical chemistry will be monitored as part of the panel of laboratory safety tests.

Potential Risk of Clinical Significance	Summary of Data/Rationale for Risk	Mitigation Strategy
Study Procedures		

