1. Using the geometric mean measured exposed individual based on study 201544 (200 µg top dose Day 1) to generate (linear extrapolation including an increase of 1.71 fold for C_{max} and 1.54-fold on AUC due to formulation differences) the exposure for a 1000 µg Inhaled dose concomitant with a 10 mcg intravenous dose (15 min infusion) (intravenous dose exposures assume 1% of inhaled exposure as worst case) based on a single dose period 1 and following a single oral dose of 800 µg in period 2 (assuming 60:40 lung to oral deposition using study data from 201544 and charcoal block and linear extrapolation). C_{max} and AUC_{0-24h} of 3.5 ng/mL and 14.7 ng.h/mL for Period 1 and a C_{max} and AUC_{0-24h} of 0.47 ng/mL and 3.7 ng.h/mL for Period 2 respectively.
2. Based on the no observed adverse event level (NOAEL) derived from the rat 3 month toxicology study R29876 with a C_{max} and AUC of 43.7 ng/mL and 286 ng.h/mL respectively.
3. Based on the highest achieved geometric mean value derived from reported trials to date of 5.3 ng/mL and 85 ng.h/mL based on exposure on Day 7 following repeat daily single doses (study PII115117).

For more detailed information on the clinical pharmacokinetics, see the GSK2269557 IB [GlaxoSmithKline Document Number [2012N141231_07](#)].

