9.4.3. Electrocardiograms

- 12-lead ECGs will be measured in a supine or semi-supine position after 5 minutes rest.
- 12-lead ECGs will be obtained at each time point during the study, as outlined in the SoA (see Section 2). This will be performed using an ECG machine that automatically calculates the heart rate and measures PR interval, QRS duration, QT, and QTcB or QTcF intervals. Refer to Section 8.1.2 for QTc withdrawal criteria and additional QTc readings that may be necessary.
- At each time point at which triplicate ECG are required, 3 individual ECG tracings should be obtained as closely as possible in succession, but no more than 2 minutes apart. The full set of triplicates should be completed in less than 4 minutes.
- Baseline will be defined as the mean of the 3 pre-dose measurements taken on Day 1 (Treatment 1).

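### In Period 1 the only Day 1 post-dose ECG and vital-sign set is at 6 h, when the protocol's own predictions put concentration at roughly 15–26% of an early peak, so it is insensitive to effects that track plasma concentration

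*Protocol*

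**What the plan says.** Footnote 3 to the Period 1 Schedule of Activities (Protocol Section 2) covers ECG and vital signs. Triplicates are taken at screening and before dosing on Day 1; after that, "single measurements will be taken at 6 h post-dose on Day 1 and at all other time points". The other columns marked for these assessments are Day -1, 24 h and 168 h. SAP Appendix 2 carries the same footnote. Protocol Section 9.4.3 adds nothing: "12-lead ECGs will be obtained at each time point during the study, as outlined in the SoA". Section 9.4 refers all safety timings to the same schedule. Period 2 follows the same pattern: "Vital signs and ECG will be taken 6 h post dose".

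The role given to these readings is in the risk table (Section 3.3.1). Against the risk of exposure to GSK2269557, the listed mitigation includes that "HR and QTc measurements will be taken, haematology and clinical chemistry will be monitored". ECG and vital-sign parameters are also secondary endpoints (Section 4), and the SAP reports change from baseline in Tables 3.10 and 3.11.

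Exposure predictions are in the footnotes to Table 1 (Section 5.5.1): "C_{max} and AUC_{0-24h} of 3.5 ng/mL and 14.7 ng.h/mL for Period 1", and for the oral period "0.47 ng/mL and 3.7 ng.h/mL for Period 2 respectively". The clinical reference is the "highest achieved geometric mean value derived from reported trials to date of 5.3 ng/mL and 85 ng.h/mL". The pre-clinical reference is the rat no-effect level, with "C_{max} and AUC of 43.7 ng/mL and 286 ng.h/mL respectively".

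**The concern.** A reading meant to mitigate exposure should include a time when exposure is high. Period 1 blood is drawn at the end of the 15-minute infusion and at 0.33, 0.5, 0.75 and 1 h, so the plasma profile will be well described early. The first ECG and vital signs come five hours after the last of those draws. The Period 1 Cmax is also the exposure for which Table 1 prints its smallest margin.

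At stake is what the secondary safety endpoint can support. If a QTcF, heart rate or blood pressure change rises and falls with plasma concentration, most of it would have gone by the first reading. Tables 3.10 and 3.11 could then look reassuring about a part of the profile that was never observed. Similarly, no scheduled ECG near the peak exists against which the QTcF withdrawal criteria of Section 8.1.2 could be applied.

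**Working it through.** **Step 1: reproduce Table 1.** Margin = reference exposure ÷ predicted exposure, all inputs from the Table 1 footnotes.

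| | Pre-clinical | Printed | Clinical | Printed |
|---|---|---|---|---|
| Period 1 Cmax | 43.7/3.5 = 12.5 | 13 | 5.3/3.5 = 1.51 | 2 |
| Period 1 AUC | 286/14.7 = 19.5 | 19 | 85/14.7 = 5.8 | 6 |
| Period 2 Cmax | 43.7/0.47 = 93.0 | 94 | 5.3/0.47 = 11.3 | 11 |
| Period 2 AUC | 286/3.7 = 77.3 | 78 | 85/3.7 = 23.0 | 23 |

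All eight agree within rounding of the inputs. The smallest is the Period 1 clinical Cmax margin, 1.51 before rounding.

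**Step 2: what the predictions imply at 6 h.** The documents give neither a 6 h concentration nor a tmax, so the 6 h value has to be derived from R = AUC(0-24h)/Cmax = 14.7/3.5 = 4.2 h. Curve shapes and half-lives below are assumptions.

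- *One exponential from the peak.* Solve (1 − e^(−24k))/k = 4.2. This gives k = 0.237/h (half-life 2.9 h) and C(6 h)/Cmax = e^(−6k) = 24%.
- *Two exponentials from the peak.* C(t)/Cmax = (1 − f)e^(−at) + f·e^(−bt), with f fixed so that the area is 4.2 h. Fast half-lives of 0.1–2 h and slow half-lives of 4–60 h give 63 combinations. C(6 h)/Cmax runs from 14.5% (1 h and 60 h, f = 0.141) to 25.9% (0.1 h and 4 h, f = 0.733), with median 19%.
- *One compartment with first-order absorption.* For tmax of 0.1, 0.25, 0.5 and 1 h the result is 23.9%, 23.7%, 23.3% and 22.4%. In this family AUC/Cmax cannot be less than e × tmax, so a ratio of 4.2 h requires tmax no later than 4.2/2.718 = 1.5 h.

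In concentration terms, 0.145 × 3.5 = 0.51 and 0.259 × 3.5 = 0.91, so about 0.5–0.9 ng/mL against a peak of 3.5 ng/mL. The ratio of 5.3 ng/mL to that 6 h level is about 6 to 10, against 1.51 at the peak.

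**Step 3: a bound that needs no curve shape.** If concentration peaks at the outset and only falls, the area over the first 6 h is at least 6 × C(6 h). It cannot exceed 14.7, so C(6 h) ≤ 14.7/6 = 2.45 ng/mL, or 70% of 3.5. Reaching this would require a flat profile to 6 h and nothing afterwards. A later peak loosens the bound: ignoring all area before a 1 h peak gives 14.7/5 = 2.94 ng/mL, or 84%.

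**Step 4: sensitivity to the scaling.** Table 1 footnote 1 scales Cmax by 1.71 and AUC by 1.54 for formulation, so the two figures do not come from one observed profile. Removing that difference gives R = 4.2 × 1.71/1.54 = 4.66 h. One exponential then gives 28%, and the two-exponential grid gives 17–29%. The conclusion does not change.

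**Step 5: Period 2 for comparison.** R = 3.7/0.47 = 7.9 h, and one exponential gives 49% at 6 h. The mismatch is smaller there, so the point is confined to Period 1.

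**The case against.** The strongest case on the other side has five parts.

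- *The margin of 2 is not a distance from harm.* It is a ratio to the highest geometric mean already reached in people. The predicted 3.5 ng/mL lies below that, the margin to the rat no-effect level is 13, and Section 3.3.1 describes the drug as well tolerated. This stands, and it limits severity. A reader might take the smallest margin in Table 1 to mean a thin safety margin; the documents do not support that.
- *The IV dose is a distraction.* Footnote 1 to Table 1 assumes that it adds 1% of inhaled exposure. This stands. It is tempting to say that the peak of a first human IV dose goes unobserved at the end of infusion, but the predicted Cmax is almost wholly inhaled. Dense early sampling is also what IV clearance and volume need, so it does not locate the inhaled peak.
- *The 6 h fraction is not a protocol figure.* Correct. It depends on an early peak and assumed shapes. The shape-free bound is much weaker.
- *Other safeguards exist.* PK sampling, laboratory tests and adverse event monitoring in residence are all planned, and Sections 9.2 and 5.1.3 allow extra safety tests. These are real, but no extra ECG is scheduled, and adverse event questioning is a poor detector of a symptomless QTcF or blood pressure change.
- *The yield is small.* Six uncontrolled participants with descriptive summaries would reveal only gross changes. This stands; it argues for a modest change rather than none.

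Moving the only Day 1 reading earlier would also be a poor remedy: it would give up the later observation and the match with the 6 h set in Period 2.

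**Conclusion.** The point holds in a limited form. Period 1 has no ECG or vital sign between the pre-dose set and 6 h. If the combined profile peaks early, the 6 h reading is taken at about 15–26% of the predicted Cmax (up to 29% after allowing for the scaling factors). The schedule is thus insensitive to an effect that tracks plasma concentration without delay, which sits badly with the mitigation role given to heart rate and QTc measurement.

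A reader might infer that the readings cannot detect any effect, or that Tables 3.10 and 3.11 are bound to show no change. Neither follows. A proportional effect would still be present at 6 h in reduced form, and a delayed or lasting one could appear at 6 h or 24 h. Nor do the Protocol and SAP contradict each other on the time: both say 6 h. What needs reconciling is that time and its stated purpose.

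The conclusion rests on the predicted Cmax and AUC in Table 1 and on an early inhaled peak. The sponsor's inhaled tmax data would settle the second. This is a worthwhile, inexpensive improvement to a secondary endpoint, not a defect in the primary mass-balance objectives.

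**What to change.** Reconcile Period 1 footnote 3 with the mitigation entry in Section 3.3.1. Keep the 6 h set and add one single ECG and vital-sign set aligned with an existing early PK time. The sponsor should choose that time from its inhaled tmax data and record the reason. Section 9 already gives the order when procedures coincide: ECG, vital signs, blood. Make the same edit in SAP Appendix 2, and report the added time in Tables 3.10 and 3.11.

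Where possible the new set should avoid the food cue. Its timing first needs settling: the schedule and Section 6.3.1 place it about 0.5 h after dosing or the start of infusion, while Section 5.1.2 counts 0.5 h from the end of the 15-minute infusion.

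The cost is one non-invasive set per resident participant and a footnote in each document. Depending on the time chosen, it may make the first hour busier, since each reading needs 5 minutes of rest between closely spaced draws. The Entero-Test string, in place until about 2.5 h, and the food cue may themselves affect heart rate and blood pressure. That should be noted when the reading is interpreted. If the sponsor keeps 6 h alone, it should justify the time against Section 3.3.1 and state in the report that the safety tables hold no near-peak reading.
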